9.4.2 UNANTICIPATED PROBLEM REPORTING

The investigator will report unanticipated problems (UPs) to the reviewing Institutional Review Board (IRB). The UP report will include the following information:

- Study Information: Title, PI, IRB#, Sponsor/award #, IND/IDE#
- Number of subjects enrolled to date and currently actively involved in research procedures.
- Date of UP, Date notified of UP
- Classification of the Experience Type: On protocol UP for subjects, Off protocol UP, or Other Unanticipated Problem
- Participant ID, if applicable
- Description of event
- Relationship of the device to the UP.
- Basis for UP determination: Analysis as to why the event represents a “problem” for the study and why it is “unanticipated”. For instances of increased frequency or severity, it must state how the frequency or severity diverges from the expected.
- Response Plan. Description of proposed actions, including modifications, to be taken by investigators in response to the UP

To satisfy the requirement for prompt reporting, UPs will be reported to the IRB within 7 calendar days of discovering the information.

10 STATISTICAL CONSIDERATIONS

10.1 STATISTICAL HYPOTHESES

Our central hypothesis is that EVAC-PU-ETT is as safe as the standard PVC-ETT and is superior to the standard PVC-ETT in reducing the occurrence of VAP and several of its long-term consequences.

The primary objectives of the proposed trial are to compare the clinical safety and effectiveness of EVAC-PU-ETT compared with PVC-ETT. The primary clinical endpoints will be: safety, quality of life, and cognitive impairment. Safety, measured as long-term laryngeal injury, will be tested for equivalence between the two treatment groups, or more precisely, that the EVAC-PU-ETT treatment is “non-inferior” to the PVC-ETT treatment. Quality of life will be assessed using the RAND Short Form Health Survey (SF-36) Physical Component Summary (PCS) and Mental Component Summary (MCS). For cognitive impairment, patients will be considered cognitively impaired if their global cognition scores are at least 1.5 standard deviation (SD) below the population mean (for comparable patients with moderate TBI) in at least two global cognition scores or more than 2 SD below the population mean for a single global cognition score. Safety will be analyzed using a sequential design with one interim analysis. The primary aims for quality of life and cognitive impairment will be evaluated for superiority of the EVAC-PU-ETT treatment using a fixed sample design. The treatment effect will be measured as the difference in probability risks, between the treatment groups, for the safety and cognitive impairment outcomes. The

treatment effect for the quantitative quality of life outcomes will be represented as differences in means.

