Aim 4. To perform economic evaluation (cost-consequence approach) of quality of life of patient and the healthcare resource utilization and cost for hospitals of EVAC-PU-ETT compared with PVC-ETT.

Endpoints:

Primary Endpoint: The study primary endpoints will be measures of quality of life, and cognitive function at 6 months after randomization. Additional endpoints include safety and ventilator associated events.

Quality of life. The patient interview will also include the evaluation of quality of life using the RAND version 1.0 of the Medical Outcomes Study 36-item Short-Form (SF- 36) General Health Survey. This instrument includes eight sub-indices of the following types: vitality, physical functioning, bodily pain, general health perceptions, physical role functioning, emotional role functioning, social role functioning, and mental health. It also includes a single item that provides an indication of perceived change in health.

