Cognitive function. At the six-month follow up, we will also assess cognitive function using a battery of tests assessing domains previously demonstrated to be potentially affected by periods of respiratory distress and validated in both normal aging and cognitively impaired populations. The core battery will consist of measures from the National Alzheimer Coordinating Center's Uniform Data Set (UDS): 1) Montreal cognitive assessment (MoCA), a global cognitive screen which has been shown to be much more sensitive than the Mini Mental Status Examination; 2) Craft Story Recall (an analogue to the Logical Memory subtest of the Wechsler Memory Scale), measuring immediate and delayed verbal contextual recall; 3) Benton Complex Figure test, which measures executive function and visuospatial ability, as well as visuospatial recall; 4) Digit Span, a test of attention and working memory; 5) Trail Making, Parts A and B, measures of attention and divided attention/working memory; and 6) semantic and phonemic verbal fluency test. Advantages of using the UDS are that it contains tests sensitive to cognitive impairment following respiratory illness that have been validated in older impaired and unimpaired populations, is freely available via the National Alzheimer Coordinating Center website, provides normative data and a normative calculator that are easily accessible online, and permits comparison with a nationwide database of older adults. Additional tests will be included to ensure specific impairments in patients with respiratory illness are adequately assessed: 1) Hopkins Verbal Learning Test-Revised – (HVLT-R), a measure of declarative verbal list learning and memory, which allows evaluation of the participant's ability to use semantic clustering strategies during recall, which may be disrupted following acute or prolonged respiratory illness; 2) Coding (previously termed "Digit symbol", from the Wechsler Adult Intelligence Scale-4th ed [WAIS-IV], 2008, PsychCorp), a measure of speed of information processing /working memory. Participants will be considered cognitively impaired if any test is 2 standard deviations or greater below the age, sex, education adjusted mean, or if two tests are 1.5 standard deviations or greater below the mean, consistent with previous studies in this area. As we will not have access to neuropsychological tests prior to illness, we will include a measure of premorbid ability, the Test of Premorbid Functioning (TOPF, 2009, PsychCorp), in order to gauge whether current performance on cognitive measures may represent a change from previous levels of function.

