	
visuospatial recall; 4) Digit Span, a test of attention and working memory; 5) Trail Making, Parts A and B, measures of attention and divided attention/working memory; and 6) semantic and phonemic verbal fluency test. Advantages of using the UDS are that it contains tests sensitive to cognitive impairment following respiratory illness that have been validated in older impaired and unimpaired populations, is freely available via the National Alzheimer Coordinating Center website, provides normative data and a normative calculator that are easily accessible online, and permits comparison with a nationwide database of older adults. Additional tests will be included to ensure specific impairments in patients with respiratory illness are adequately assessed: 1) Hopkins Verbal Learning Test-Revised – HVLT-R), a measure of declarative verbal list learning and memory, which allows evaluation of the participant's ability to use semantic clustering strategies during recall, which may be disrupted following acute or prolonged respiratory illness; 2) Coding (previously termed "Digit symbol", from the Wechsler Adult Intelligence Scale-4th ed [WAIS-IV], 2008, PsychCorp), a measure of speed of information processing /working memory. Participants will be considered cognitively impaired if any test is 2 standard deviations or greater below the age, sex, education adjusted mean, or if two tests are 1.5 standard deviations or greater below the mean, consistent with previous studies in this area. As we will not have access to neuropsychological tests prior to illness, we will include a measure of premorbid ability, the Test of Premorbid Functioning (TOPF, 2009, PsychCorp), in order to gauge whether current performance on cognitive measures may represent a change from previous levels of function.

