Specifically, we will evaluate whether there is a difference in the laryngeal injury risk probabilities for the two treatments, we will use maximum likelihood estimation (binomial family) with an identity link function. The statistical model used for this analysis will be: $p(X) = \beta_0 + \beta_1 X$ where $p(X)$ denotes the laryngeal injury probability and X is an indicator denoting the treatment assignment (1 = EVAC-PU-ETT, 0 = PVC-ETT). The identity link function makes the interpretation of parameter for the treatment effect, β_1 , be equal to $\beta_1 = p(1) - p(0)$, which is exactly the risk difference, q , noted above. In the Prevent pilot study, the estimated risk of laryngeal injury was 0.39 for the PVC-ETT treatment group and 0.38 for the EVAC-PU-ETT treatment group. Assuming an estimated risk difference less than or equal to 0.05 for the targeted sample size of $N=1074$ (537 patients per treatment arm) for the pre-specified alpha-level and statistical design, the statistical power for concluding non-inferiority of the EVAC-PU-ETT treatment group would be 80 percent.

Analysis of Quality of Life Primary Endpoint

We will evaluate whether there are differences in quality of life measures between treatment groups by comparing mean scores. Separate analyses will be conducted for the two endpoints. The statistical model will be linear regression, $\mu(X) = \beta_0 + \beta_1 X$, where $\mu(X)$ denotes the mean SF-36 score, X is an indicator denoting the treatment assignment as before. The test for a treatment effect is denoted by, $\beta_1 = \mu(1) - \mu(0)$. We will use robust inference so that our tests will be valid for modest departures in modeling assumption. Additionally, we will transform the scores to reflect “percent of healthy life”. This transformation of the SF-36 measures provides easily interpretable variables and allow for the retention of patients that die during the study. As noted previously, the design for this endpoint is a fixed sample design. To have power of at least 80 percent for the targeted sample size of $N=1074$, we require a difference in the means to be greater than 0.17 standard deviations on a standardized scale. These

power and effect size calculations assume an independent, two-sample test, an alpha level of five percent and all statistical tests are two-sided tests.

Analysis of Cognitive Impairment Primary Endpoint

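### Section 10.1 scores cognitive impairment against a moderate-TBI mean, Sections 2.1 and 4 against age-, sex- and education-adjusted norms, and Section 10.4.2 does not say which rule applies

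*Combined protocol and SAP*

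**What the plan says.** Cognition at six months is presented as primary in the endpoint text of Sections 2.1 and 4 ("The study primary endpoints will be measures of quality of life, and cognitive function at 6 months after randomization") and has its own analysis heading in Section 10.4.2 ("Analysis of Cognitive Impairment Primary Endpoint"). The aims text of the same two sections describes the proportion impaired as an additional endpoint. Even so, the endpoint has its own hypothesis, power statement and model.

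Impairment is defined in two ways.

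- **Sections 2.1 and 4**, in matching words. The first limb is: "Participants will be considered cognitively impaired if any test is 2 standard deviations or greater below the age, sex, education adjusted mean". The second is: "or if two tests are 1.5 standard deviations or greater below the mean, consistent with previous studies in this area". The battery is listed: the Uniform Data Set (UDS) tests, the HVLT-R and WAIS-IV Coding. For the UDS, the text says that it "provides normative data and a normative calculator that are easily accessible online".
- **Section 10.1.** The two-score limb is "at least 1.5 standard deviation (SD) below the population mean (for comparable patients with moderate TBI) in at least two global cognition scores". The single-score limb is "more than 2 SD below the population mean for a single global cognition score".

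Section 10.4.2 models the risk of cognitive impairment with a binomial model and identity link. It neither defines impairment nor points to a definition. Section 10.2 assumes a prevalence of 0.40 without tying it to either rule.

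**The concern.** A binary endpoint is only as well defined as the rule that turns scores into yes or no. Section 10.1 is where an analyst would look for that rule, and its reference group does not fit the trial. Section 6.1 admits patients who need emergency intubation for acute respiratory distress or failure. In the readable text, traumatic brain injury appears otherwise only in the abbreviation list.

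An analyst who followed Section 10.1 literally would score an endpoint that the plan analyses as primary against a different population from the one named in the endpoint sections. Two careful analysts could produce different event counts from the same test scores, each with a section of the plan to cite.

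**Working it through.** **The two rules side by side**

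| Feature | Sections 2.1 and 4 | Section 10.1 |
|---|---|---|
| Scores that count | any test of the listed battery | global cognition scores, not listed |
| Reference mean | adjusted for age, sex and education | population mean; moderate TBI named in the two-score limb |
| One low score | 2 SD or more below | more than 2 SD below |
| Two low scores | 1.5 SD or more below | 1.5 SD or more below |

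The structure and the 1.5 SD cut-off agree. The other three features differ.

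**1. Reference mean (main conflict).** Measure a score in SD units from the adjusted norm. Assume that the TBI mean lies d units below that norm, with the same SD, and that both limbs of Section 10.1 use it. The Section 10.1 cut-offs then fall at 2 + d and 1.5 + d below the adjusted norm. The documents give no value for d, so these are illustrations only:

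- d = 0: cut-offs 2.0 and 1.5, so the reference makes no difference.
- d = 0.5: cut-offs 2.5 and 2.0.
- d = 1.0: cut-offs 3.0 and 2.5.

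Take a patient whose only low result is a memory test 2.5 SD below the adjusted norm. Sections 2.1 and 4 call this patient impaired. Under Section 10.1 with d = 1.0 the score is 2.5 − 1.0 = 1.5 SD below the reference mean. It is the only low score, so the patient is not impaired.

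**2. Scores that count (softer conflict).** The only test described as global is the "Montreal cognitive assessment (MoCA), a global cognitive screen"; the others are described by domain. If the memory test in the example is not a global score, the patient is not impaired under Section 10.1 even at d = 0. If the phrase is loose wording for the whole battery, this difference disappears.

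**3. Boundary (minor).** With the same tests and the same mean, a single score exactly 2.0 SD below counts in Sections 2.1 and 4 but not in Section 10.1. No other value is affected.

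**The plan's own power figure.** Inputs from Section 10.2: n = 537 per arm, control risk p0 = 0.40, difference 0.09 (so p1 = 0.31), two-sided 5%, power at least 80%. With p̄ the mean of the two risks and Φ the standard normal distribution function:

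power = Φ{[(p0 − p1) − 1.96 × SE0] / SE1}

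- SE0 = √(2 × 0.355 × 0.645 / 537) = 0.02920
- SE1 = √[(0.40 × 0.60 + 0.31 × 0.69) / 537] = 0.02907
- power = Φ[(0.09 − 0.05724) / 0.02907] = Φ(1.127) = 0.870

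For a 0.09 reduction over the plan's own prevalence range of 0.2 to 0.8, power is lowest at 0.545 against 0.455. There SE0 = √(2 × 0.5 × 0.5 / 537) = 0.03051 and SE1 = √(2 × 0.545 × 0.455 / 537) = 0.03039. Power = Φ[(0.09 − 0.05981) / 0.03039] = Φ(0.993) = 0.840. The claim of at least 80% holds throughout, with complete data.

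**The case against.** The rules share a skeleton: one score at 2 SD or two at 1.5 SD. The TBI remark occurs once and may be a leftover, while the adjusted-norm rule is stated twice, in the sections that define the endpoint. A sensible analyst would probably use that one. Appendix V and the references after number 90 are not in the readable text and may list the scores and norms. Power is unaffected.

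Much of this stands, and it limits the point. Several stronger readings are tempting but not supported:

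- *The two-score limb can never be met, because only the MoCA is global.* Section 10.1 uses the plural and asks for at least two, so its author had several scores in mind.
- *The statistics chapter gives no rule.* It does, in Section 10.1. The silence is in Section 10.4.2.
- *The plan has no TBI values or score list anywhere.* That cannot be said without the appendices.
- *The unattached 0.40 undermines the sample size.* For an absolute difference of 0.09, it does not.
- *A statistician holding device labels A and B will choose between the rules.* Nothing in the documents suggests this. Fixing the rule before any comparison by arm is ordinary pre-specification.

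What does not go away is that the body of the plan contains two rules with different reference populations. A list of tests in an appendix would not remove that, and calling the TBI remark a leftover is a guess about intent.

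**Conclusion.** The plan holds two conflicting definitions of cognitive impairment. The difference in reference population is clear on the face of the text; the difference in which scores count is possible; the boundary difference is trivial in scope but real. They can classify the same patient differently, and the primary analysis section does not choose between them.

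The effect on the event rate or the treatment comparison cannot be computed, because the readable text gives neither moderate-TBI means and SDs nor a list of global scores. The stated power is sound: about 87% at 0.40 against 0.31, and at least 84% over the plan's range for a 0.09 reduction. The conclusion rests on the body text alone. The documents do not settle which rule the sponsor intended, though the adjusted-norm rule has the better textual support. Because a stated rule conflicts with another for an endpoint analysed as primary, it needs to be settled before cognitive outcomes are compared by arm.

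**What to change.** Before any comparison of cognitive outcomes by arm, the sponsor should confirm the intended rule and record it in the formal addendum that Section 10.2 provides for. The proposed default is the rule in Sections 2.1 and 4, since it is given twice in the endpoint sections and names tests and norms. If the sponsor confirms it:

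- Delete the moderate-TBI reference and the global-score wording from Section 10.1.
- State there that a participant is impaired if any listed test is 2 SD or more below the age-, sex- and education-adjusted mean, or if two listed tests are each 1.5 SD or more below that same mean.
- Cite this rule in the cognitive analysis of Section 10.4.2.

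The cost is a one-paragraph addendum with no change in sample size. It should not be assumed that no further data are needed. The rule requires education, which is absent from the demographics listed in the Schedule of Activities (Section 2.3, footnote 3) and in Section 9.1. It may be on the Appendix V forms, which cannot be checked here. The sponsor should confirm that education is recorded for all participants, including the first 90, who have already completed follow-up.

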10.2 SAMPLE SIZE DETERMINATION

Power and Sample Size Determination

The trial uses a fixed sample design. We assumed a prevalence of cognitive impairment of 0.40 for this at population, a sample size of N=1074, we require a minimum risk difference of 0.09 ($q = p_1 - p_0 < -0.09$) to attain statistical power of at least 80 percent. We assumed a prevalence of cognitive impairment of 0.40, however, the risk difference of 0.09 attains the targeted level of power or higher, for a prevalence in a reasonable range (e.g., 0.2-0.8). To achieve power of at least 80 percent for the targeted sample size of N=1,074, we require a difference in the means to be greater than 0.17 standard deviations on a standardized scale. For the SF-36 mental component summary (MCS), for example, if the SD is conservatively equal to 30, then the minimum difference in the mean MCS scores will need to be approximately 5.1 points (i.e., min difference = $0.17 * SD = 0.17 * 30$). For the physical component summary (PCS), if the population SD were 40 points, the minimum difference would be 6.8 points (min difference = $0.17 * 40$). These power and effect size calculations assume an independent, two-sample test, an alpha level of five percent and all statistical tests are two-sided tests.

The target sample size for the study is 1,074 patients (537 per treatment arm), in order to achieve power of 80% for each test of the primary outcomes. The study is powered for meaningful minimum effect sizes to detect treatment differences in the primary endpoints. The statistical software STATA vers. 15 (Stata Corporation, College Station, TX) and R have been used to compute the statistical power.

Based on 2016 data, emergency intubations occurred primarily in the Emergency Department (ED) and in the hospital: approximately 200 intubations were performed in the ED and 404 intubations occurred in the hospital, yielding approximately 600 emergency intubations per year. With a projected enrollment period of 36 months, we anticipate adequate feasibility to accrue the required sample size.

Missing Data

The primary analysis described above provides valid inference if the missing response data is missing at random (MAR). However, in the case that the data are not missing at random (NMAR), the results of the proposed analyses may be biased. We will perform sensitivity analyses to assess the impact of the missing outcome data. We will employ standard multiple imputation methods to assess the degree to which the primary analysis may be affected by the missing data. Patient retention will be key to the successful completion of this study, and we will take several measures to maximize retention. We expect missing data due to “losses to follow up” to be minimized by our efforts. We will make every reasonable effort to retain the patients through follow-up to preserve the integrity of the study and to minimize

possible bias associated with loss due to dropouts. We realize that these investigations of missing data or accruing additional patients to meet targeted sample sizes are not foolproof substitutes to remedy missing data.⁸ We intend to make every reasonable attempt to maximize the rate of follow up in our sampled population. We will minimize the loss of follow-up data by continuing to have clear performance standards in the protocols to achieve high quality trial conduct, including high levels of data capture. We will continue to monitor and carefully educate providers as well as patients or their representatives during the informed consent process regarding the scientific relevance, and we will also monitor data collection to ensure quality standards are met, including targeted levels of data capture.

Changes to the Statistical Analysis Plan

Changes to this statistical analysis plan will be documented via a formal addendum that includes rationale, new procedures, and potential differences from prior plan.

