Pneumonia has negative effects on quality of life including physical functioning, general health, and vitality even long after recovery from disease.^{28, 29} With preexisting comorbid conditions, several domains of the SF-36 scores (physical function, physical role function, general health, and vitality) were significantly lower at 12 or 18 months, and were even worse when pneumonia was associated with sepsis.^{30, 31} Similar negative physical and mental effects have been observed in survivors of acute respiratory distress syndrome (ARDS),³²⁻³⁴ and in sepsis survivors.³¹ It is also well documented that critical illness alone is associated with a decrease in long-term quality of life among previously healthy older patients admitted to a medical ICU.³⁵ Furthermore, several reports suggest that persistent voice disorders, possibly related to airway complications, are associated with reduced quality of life in the domains of physical functioning, emotional well-being and social functioning.³⁶⁻³⁸

Likewise, pneumonia, sepsis, and acute lung injury have a negative and lasting effect on cognitive function and have been associated with increased risk of dementia in some studies.^{31, 39-41} In a longitudinal cohort of the EDEN trial – where over 80% had pneumonia or sepsis as ARDS risk factor – 20 to 30% demonstrated cognitive impairment.^{33, 34} Importantly, cognitive impairment has been identified as one of the outcomes patients were least willing to accept.⁴² Considering this growing body of clinical and experimental evidence suggesting that systemic infection, especially pneumonia, can lead to long-term effects on quality of life and cognitive function,^{31, 39-41, 43} interventions aimed at VAP prevention have the potential to greatly impact and improve clinical care and patient quality of life.

VAP is preceded by bacterial colonization of the trachea in most cases.^{1, 44-48} The source of colonization is likely to be bacterial contamination of oropharyngeal secretions that leak through folds in the endotracheal tube (ETT) cuff into the trachea.^{46, 49-51} Microaspiration below an inflated high-volume, low pressure ETT cuff has been shown to occur in virtually 100% of cases,^{49, 51} and it is reduced in the semi-recumbent position.⁵²⁻⁵⁵ Interventions that prevent tracheal microaspiration reduce the incidence of VAP.^{63, 64}

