
occurring during the ICU stay from enrollment until ICU discharge. An IVAC event is defined by a 14-day period, starting on the day of onset of worsening oxygenation. For this study, we will use the CDC proposed tiered approach algorithm that encompasses ventilator associated conditions (VAC), infection related ventilator-associated complication (IVAC), and possible VAP.
 
Step 1: VAC (≥1 required):
 
 1) Daily min FiO_2 increase ≥ 0.20 (20 points) for ≥ 2 days - OR 2) Daily min PEEP increase $\geq 3 \text{ cm H}_2\text{O}$ for ≥ 2 days (after two days of stable or decreasing daily minimum values) 
Step 2: IVAC:
 
 1) Temperature $>38.0^\circ\text{C}$ OR $<36.0^\circ\text{C}$ - OR 2) White blood cell count $\geq 12,000$ or $\leq 4,000 \text{ cells/mm}^3$ - AND 3) A new antimicrobial agent is started and is continued for ≥ 4 days. 
Step 3: Possible VAP:
 
Criterion #1: Positive cultures of one of the following specimens collected within $+\/- 2$ days of onset of VAC, meeting quantitative or semi-quantitative thresholds, without requirement for purulent respiratory secretions: 1) Endotracheal aspirate; 2) Bronchoalveolar lavage; 3) Protected specimen brush; 4) Lung tissue - OR
 
Criterion #2: Purulent respiratory secretions AND a positive culture of one of the following specimens (qualitative culture, or quantitative/semi-quantitative culture without sufficient growth to meet Criterion #1): 1) Sputum; 2) Endotracheal aspirate; 3) Bronchoalveolar lavage; 4) Lung tissue; 5) Protected specimen brush.
 
Other secondary endpoints related to VAP
 
 1) Incidence of ventilator-associated events (VAEs); 2) Respiratory antimicrobial use; 3) VAP risk using a "clinical" definition for interpretation of the study findings in the context of previous literature where clinical definitions were used; 4) Occurrence of early- versus late-onset IVAC and time to first IVAC event. Early-onset IVAC is defined as IVAC occurring within four days of tracheal intubation while late-onset VAP is defined as VAP occurring 5 days or later. 
Additional secondary clinical endpoints
 
 1) 28-day ventilator-free days; 2) Daily Sequential Organ Failure Assessment (SOFA) score; 3) Length of ICU and hospital stay; 4) In-hospital and 6-month mortality comparison between the two groups.

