8.2 PARTICIPANT DISCONTINUATION/WITHDRAWAL FROM THE STUDY

Subjects may be withdrawn from the study at their own request or at the request of their legally acceptable representative, or in case of inadvertent enrollment.

Individuals enrolled in the study who become incidentally incarcerated after enrollment will be withdrawn from continued participation until they are no longer incarcerated.

Participants will not be replaced if they withdraw after initial enrollment, and the data will be collected and included in the analysis up to the time of withdrawal.

A patient who is inadvertently enrolled fails to meet eligibility criteria; subjects inadvertently enrolled will be withdrawn from the study and their data removed. They are not considered a subject of planned enrollment.

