To evaluate whether there is a difference in the risk of cognitive impairment between the two treatments, we will use the same fixed sample methods used for the primary safety endpoint. We will estimate the difference in the probability of cognitive impairment for the two treatments using maximum likelihood estimation (binomial family) with an identity link. We will use robust (sandwich) standard error estimates in the test statistics and confidence intervals to remedy possible minor violations of modeling assumptions. The design for this endpoint is a fixed sample design. We assumed a prevalence of cognitive impairment of 0.40 for this at population, a sample size of N=1074, we require a minimum risk difference of 0.09 ($q = p_1 - p_0 < -0.09$) to attain statistical power of at least 80 percent. We assumed a prevalence of cognitive impairment of 0.40, however, the risk difference of 0.09 attains the targeted level of power or higher, for a prevalence in a reasonable range (e.g., 0.2-0.8).

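### Section 10.2 makes no allowance for deaths or losses: 80% power fails for both quality-of-life tests under material attrition, and for cognition holds only to about 18% unevaluable at 0.40 vs 0.31

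*Combined protocol and SAP*

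**What the plan says.** Section 10.2 fixes the target at 1,074 patients, 537 per arm, "in order to achieve power of 80% for each test of the primary outcomes". Tests are two-sided at 5%.

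- **Quality of life (SF-36 PCS and MCS).** Sections 10.2 and 10.4.2 both say that, at this sample size, "we require a difference in the means to be greater than 0.17 standard deviations on a standardized scale". Section 10.2 converts this to 5.1 MCS points (SD 30) and 6.8 PCS points (SD 40).
- **Cognitive impairment.** With an assumed prevalence of 0.40, "we require a minimum risk difference of 0.09" for at least 80% power. The same difference is said to suffice for prevalences from about 0.2 to 0.8.
- **Missing outcomes.** The missing-data text in Section 10.2 says the primary analysis is valid under missing at random, describes retention efforts, and reserves multiple imputation for sensitivity analysis. It gives no expected rate.
- **Withdrawals.** Section 8.2: "Participants will not be replaced if they withdraw after initial enrollment".
- **Deaths.** Section 4 lists as a secondary endpoint "In-hospital and 6-month mortality comparison between the two groups". Section 10.4.2 adds a transformed quality-of-life score that would "allow for the retention of patients that die during the study", with no SD or power for it. Nothing comparable is given for cognition.

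The only numerical loss figure is the 40% in the synopsis under Study Duration. It concerns ineligibility and exclusions during accrual, not follow-up.

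**The concern.** PCS, MCS and the cognitive battery are all collected at one in-person visit six months after randomization (Sections 5.4 and 9.1). The patients were intubated as emergencies and admitted to intensive care, mostly without prior consent. Some will die, and some patients or their representatives will decline to continue, at which point data collection stops (Section 11.1.1.2). Others will not be reached. The regression models in Section 10.4.2 can use only patients with an outcome, so the primary tests will run on fewer than 537 per arm.

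If the quoted power is the complete-data figure, the real power for quality of life is lower than the plan states, and a null result would be read against a sensitivity the trial did not have. The harm is lost power. It is not false exclusion of effects, because exclusion would be read from a confidence interval based on the patients actually observed. For cognition, the reader cannot tell how much loss the stated power tolerates.

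**Working it through.** **Inputs from the plan:** two-sided alpha 0.05; 537 per arm; 0.17 SD for each quality-of-life score; SDs 30 (MCS) and 40 (PCS); cognition difference 0.09 at prevalence 0.40.

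**Assumptions made here:** 10, 20, 30 or 40% of patients unevaluable, equally in both arms; 0.40 taken as the control rate. Normal approximation throughout, with n = 537 × evaluable fraction.

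**Step 1. Reproduce the plan's quality-of-life figure.**

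Detectable difference at 80% power = (1.960 + 0.842) × √(2/n). At n = 537 this is 2.802 × 0.0610 = 0.171 SD.

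Power at d = 0.17 is Φ(d√(n/2) − 1.960). At n = 537 this is Φ(2.786 − 1.960) = 79.5%.

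Exactly 80% needs 2 × (2.802/0.17)² ≈ 543 per arm. The gap between 79.5% and 80% is rounding, not an error. It does show that 0.17 SD assumes every enrolled patient is evaluable.

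**Step 2. Reproduce the cognition figure.**

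Power = Φ(0.09/SE − 1.960), with SE = √[(p₁(1−p₁) + p₀(1−p₀))/n].

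For 0.40 vs 0.31 at n = 537, SE = √[(0.2400 + 0.2139)/537] = 0.0291. Power is Φ(3.096 − 1.960) = 87.2% (87.0% with pooled variance), consistent with the plan's claim of at least 80%.

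**Step 3. Repeat at the evaluable number.**

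| Unevaluable | n per arm | QoL power at 0.17 SD | QoL detectable (SD) | MCS points (SD 30) | PCS points (SD 40) | Cognition power, 0.40 vs 0.31 | Cognition detectable (points) |
|---|---|---|---|---|---|---|---|
| 0% | 537 | 79.5% | 0.171 | 5.1 | 6.8 | 87.2% | 8.2 |
| 10% | 483 | 75.3% | 0.180 | 5.4 | 7.2 | 83.6% | 8.6 |
| 20% | 430 | 70.2% | 0.191 | 5.7 | 7.6 | 79.1% | 9.1 |
| 30% | 376 | 64.5% | 0.204 | 6.1 | 8.2 | 73.6% | 9.7 |
| 40% | 322 | 57.8% | 0.221 | 6.6 | 8.8 | 66.9% | 10.4 |

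A true 0.17 SD effect would therefore be missed in about 25, 30, 36 or 42% of such trials, against the 20% that the plan implies.

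**Step 4. Loss that cognition tolerates before a 9-point difference drops below 80% power.**

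Required n per arm = 7.849 × [p₁(1−p₁) + p₀(1−p₀)]/0.09². Tolerated loss = 1 − n/537.

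| Control vs EVAC-PU-ETT | n per arm for 80% | Tolerated loss |
|---|---|---|
| 0.20 vs 0.11 | 250 | 53% |
| 0.30 vs 0.21 | 364 | 32% |
| 0.40 vs 0.31 | 440 | 18% |
| 0.50 vs 0.41 | 477 | 11% |

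At 0.40 vs 0.31 the pooled formula gives 17.5% and a continuity correction 13.4%.

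**The case against.** The strongest reply is that every efficacy figure in Section 10.2 reproduces, so the plan contains an undeclared assumption rather than a miscalculation. That is true. But the plan goes beyond a conditional calculation: it says the enrolment target delivers 80% power for each primary test, and for quality of life that holds only if nobody is lost.

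Specific points:

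- **SD called conservative.** Section 10.2 describes the MCS SD of 30 that way. If the true SD is smaller, the point targets survive some loss: at 20% unevaluable, 5.1 MCS points stay detectable up to an SD of 5.1/0.1912 = 26.7, and 6.8 PCS points up to 6.8/0.1912 = 35.6. This stands for the point values, although the documents do not support any particular SD and do not call the PCS value conservative. It does not help the 0.17 SD claim, which is already standardized.
- **Score that keeps deaths.** If this is the primary quality-of-life analysis, only withdrawals and losses reduce n and the tabulated MCS and PCS points do not apply. The plan introduces it as an addition to the SF-36 means and gives no basis for its power.
- **Meaning of 0.40.** The plan does not say which rate this is. Tolerated loss is about 14% if it is the average of the arms and 11% if it is the EVAC-PU-ETT rate. It is larger at lower control rates: Section 3.2 cites an ARDS follow-up cohort in which "20 to 30% demonstrated cognitive impairment", and control rates of 0.30 and 0.20 tolerate 32% and 53%. So cognition has real slack, of undeclared and variable size.
- **Retention.** Sections 6.4 and 8.3 describe serious efforts, including home visits, payment and alternate contacts. They may limit loss among survivors. They cannot prevent deaths, and they supply no number.

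**Conclusion.** The concern holds. The plan ties 80% power to the enrolled number and declares no allowance for deaths or losses.

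For PCS and MCS there is no reserve on the standardized scale: 5% unevaluable already gives 77.5%, and 20% gives 70%. For cognition at 0.40 vs 0.31, complete-data power is 87% and 80% is kept to about 18% unevaluable; the limit moves to 11% at 0.50 vs 0.41 and 53% at 0.20 vs 0.11.

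The absence of an allowance is a matter of record. The size of the shortfall rests on assumed attrition, equal loss in the two arms, the SF-36 means in evaluable patients as the primary quality-of-life analysis, and 0.40 as the control rate. Safety, which Section 10.1 also calls primary, is not covered here. This should be fixed, but it does not call the choice of tests or the analysis set into question.

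**What to change.** Keep 1,074 enrolled and revise Sections 10.2 and 10.4.2:

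1. State the assumed 6-month mortality and, separately, the assumed withdrawal and loss. The first 90 patients have completed follow-up (Section 5.1), so their pooled, arm-blinded rates can inform this. Show a short range: a 30% rate in 90 patients has a 95% half-width of 1.96 × √(0.3 × 0.7/90) = 9.5 points, and those patients came from OHSU whereas the other 984 are to come from YNHH.
2. Give power and detectable differences for PCS, MCS and cognition at the resulting evaluable number.
3. State whether the SF-36 score or the transformed score that keeps deaths is the primary quality-of-life analysis, and base its power on the SD of that score.
4. Say which arm's rate 0.40 represents and how much loss the cognition calculation tolerates at that rate.
5. Remove the claim of 80% power for every primary test, or tie it to the larger detectable differences.

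The cost is protocol and SAP wording, with no change to sample size, tests or analysis set. The stated figures become less favourable, and the assumed attrition may prove wrong, which is why a range is needed.
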